10.3 STUDY METHODS AND TECHNIQUES

In addition to the standard medical and laboratory assessments, the subjects will undergo specific systemic and ophthalmological examinations. The methods and techniques that will be used in this clinical trial are listed below in [Table 1](#).

Table 1. Study Assessments

Assessment	Time points	Primary Endpoints/ Safety	Efficacy Endpoints of Clinical Relevance
Best-Corrected Visual Acuity (BCVA)-ETDRS Retro illuminated 4-meter ETDRS Chart “R” for refraction followed by Chart “1” and “2” BCVA is reported in number of letters read correctly. First, the right eye is tested with Chart 1 and then the left eye is tested with Chart 2. Must be conducted by trained examiner (technician acceptable) and as per “BCVA Instructions Manual”.		√	√
Low Luminance Best Corrected Visual Acuity LL BCVA is measured by placing a 2.0-log-unit neutral density filter over the trial frame in front of the study eye and having the participant read the normally illuminated ETDRS chart using a different version of the chart. This test is optional as subjects with low vision will not be able to perform this test and is not applicable for Cohorts 1-3.			√
Spectral Domain Optical Coherence Tomography (SD-OCT) Images obtained by certified examiner (technician acceptable). Reading of images done by central reading center. Refer to Central Reading manual for instructions.		√	√

Assessment	Time points	Primary Endpoints/ Safety	Efficacy Endpoints of Clinical Relevance
[REDACTED]	[REDACTED]	√	
Dilated Fundus Examination (peripheral retina, macula, choroid, optic nerve, retinal/detachment, retinal or vitreous hemorrhage, vitreous hemorrhage density, vitreous cells.)	[REDACTED]	√	
Microperimetry Automated microperimetry to be performed in Cohort 3 (optional) and in Cohort 4. Must be conducted by certified examiner (technician is acceptable). Reading of images done by central reading center. Refer to Central Reading manual for instructions.	[REDACTED]	√	√
Fluorescein Angiography (FA) Standard procedure for detection of CNV. Must be conducted by certified examiner (technician is acceptable): at [REDACTED] to verify dry AMD and absence of neovascular (wet) AMD, and on final exam at end of study; optional FA during follow-up in cases of suspected conversion to wet AMD	[REDACTED]	√	
Intraocular Pressure (IOP) One IOP measurement per eye	[REDACTED]	√	
Slit Lamp Examination (Lids/Lashes, Conjunctiva, Cornea, Iris, Aqueous Cells, Aqueous Flare and Lens) Must be conducted by certified examiner (technician is acceptable)	[REDACTED]	√	
Physical Examination including ECG, Vital Signs Clinical evaluation by the study-dedicated investigator or designee will be performed at several time points to evaluate pre- and post-implantation subject condition including immunosuppression treatment safety (see below)**	[REDACTED]	√	
Malignancy Assessment In the case of any suspected malignancies at screening, subject should be referred to appropriate medical specialist.	[REDACTED]	√	
Complete Blood count (including differential) / Chemistry (including Serum Electrolytes) / Coagulation / Urinalysis	[REDACTED]	√	

Assessment	Time points	Primary Endpoints/ Safety	Efficacy Endpoints of Clinical Relevance
Serology Assessment including testing for HIV, CMV, EBV, HBV and HCV	[REDACTED]	√	
[REDACTED]	[REDACTED]	√	
Immunology HLA-typing will be performed during [REDACTED] or during one of the subsequent visits if not performed during [REDACTED]	[REDACTED]	√	
[REDACTED]	[REDACTED]	√	
QuantiFERON (state of inoculation) To detect tuberculosis (TB) disease	[REDACTED]	√	
[REDACTED]	[REDACTED]	√	
Fundus Autofluorescence Imaging (FAF) Images obtained by certified examiner (technician acceptable). Reading of images done by central reading center. Images are done by using blue light Heidelberg instrumentation. Each assessment for each subject must be done with the same camera used at Screening. Refer to Central Reading manual for instructions.	[REDACTED]	√	√
Color Fundus Photography (CFP) Images obtained by certified examiner (technician acceptable). Reading of images done by central reading center. Color Images are done by using Zeiss instrumentation. Each assessment for each subject must be done with the same camera used at Screening. Refer to Central Reading manual for instructions.	[REDACTED]	√	√
Reading Speed Test This test is mandatory for subjects are proficient in English.	[REDACTED]		√
NEI VFQ-25 Quality of Life (examiner version) 25 item subject reported outcome. Scores range from 0-100 with the higher score indicating better visual function.	[REDACTED]		√

Assessment	Time points	Primary Endpoints/ Safety	Efficacy Endpoints of Clinical Relevance

Functional Reading Independence (FRI) Index The FRI index is a patient-reported outcome measure developed specifically for use in GA subjects. Scores derived from the index range from 1 (unable to do) to 4 (total independence) and may be analyzed as either categorical (which is preferred from a regulatory perspective) or continuous variables. This test should be administered in the subject's mother tongue language and is not applicable for Cohorts 1-3
	
[REDACTED]
		
√

The schedule of assessments for screening and first year during the study are detailed in [Table 2](#). The schedule of assessments for long-term follow-up is detailed in [Section 15](#).

Visit #	
Day (or M=month=28)	
General (continued)	
General safety assessment (AEs and concomitant medication)	
Surgery of OpRegen® implantation	
Investigators global evaluation of device performance	
Intraoperative Video/OCT Imaging	
Discharge from the hospital ¹⁵	
Functional Testing	
BCVA	
Low Luminance BCVA ¹⁶	
SD- OCT (central reading)	
Fundus Autofluorescence (FAF) (central reading)	
Color Fundus Photography (CFP) (central reading)	
Microperimetry ¹⁷ (central reading)	
Fluorescein Angiography (FA) (central reading)	

¹³ The eye chosen for OpRegen implantation will be the eye with worse visual function.

¹⁴ Investigators global evaluation will be determined pre- and post-implantation for participants in cohort 4 who receive subretinal cell delivery of OpRegen via [REDACTED]

¹⁵ Hospitalization is not applicable for U.S subjects.

¹⁶ Performance of Low Luminance BCVA is dependent on subject's BCVA. This test is optional for cohort 4 subjects with low vision who are not able to perform this test and is not applicable for cohorts 1-3.

¹⁷ Microperimetry for cohort 3 [optional], but is required for all [REDACTED] subjects and all cohort 4 US-treated subjects

At screening, a full ocular history will be obtained and an ophthalmic examination including the following assessments will be performed, as detailed in [Table 2](#):

- Demographics
- Inclusion/Exclusion Criteria
- BCVA
- Low Luminance BCVA (optional)
- SD-OCT (central reading)
- Microperimetry (central reading) cohort 3 [optional], but is required for all [REDACTED] subjects and all cohort 4 US-treated subjects and Cohort 4)
- Fluorescein Angiography (FA) (central reading)
- Fundus Autofluorescence (FAF) (central reading)
- Color Fundus Photography (CFP) (central reading)
- Dilated Fundus Examination
- IOP
- Slit Lamp Exam
- Reading Speed Test (for subject's proficient in English)

Final decision for subject eligibility upon confirmation of Central Reading Center and the Sponsor.

Immunosuppression therapy will be prescribed, if subject is eligible for enrollment, as detailed in [Section 9.3.1](#). [REDACTED] will be measured during the [REDACTED].

General Safety Assessment including prior and concomitant medications and adverse events will be performed during all visits.

[REDACTED]

- LOCS III (baseline 1)

[REDACTED]

11.3.1 [REDACTED]

The subjects can be hospitalized (if country specific requirement) [REDACTED] per investigator discretion. The following procedures and assessments will be performed on the [REDACTED]:

- General safety assessment (AEs and concomitant medication)
- Vital signs
- Medical History
- Physical examination
- Dilated Fundus Examination
- IOP

- Slit Lamp Exam
- SD-OCT (central reading)
- FAF (central reading)
- CFP (central reading)
- Immunosuppression assessment
- [REDACTED]
- BCVA
- Low Luminance BCVA (optional for cohort 4 subjects with low vision who are not able to perform this test and is not applicable for cohorts 1-3)
- Complete Blood count (including differential)
- Chemistry (including Serum Electrolytes)
- Coagulation – and confirmation that aspirin/aspirin containing drugs and other coagulation modifying drugs were discontinued
- Urinalysis
- Reading speed test, if not performed during Screening for subject's proficient in English
- HLA-typing will be performed during [REDACTED] or during one of the subsequent visits if not performed during [REDACTED].

[REDACTED]

[REDACTED]

The results will be reviewed by the associated principal investigator to re-confirm subject's eligibility.

[REDACTED]

[REDACTED]

The following procedures and assessments will be performed on the [REDACTED] prior to implantation:

- General safety assessment (AEs and concomitant medication)
- Vital signs
- Dilated Fundus Examination (optional)
- IOP (optional)
- Slit Lamp Exam (optional)
- [REDACTED]

[REDACTED]

11.3.2.4 Surgical Procedure and Implantation of OpRegen®

The eye chosen for OpRegen® implantation will be the eye with worse visual acuity. The surgery will be performed by retro-bulbar or peribulbar anesthetic block or monitored intravenous sedation or by general anesthesia, at the discretion of the surgeon and in discussion with the subject. The eye undergoing surgery will be prepped and draped in sterile fashion according to the institutional protocol.

OpRegen® Subretinal Implantation with Vitrectomy

Vitrectomy procedure is required in the majority of cases in which retinal or sub-retinal intervention is performed. It is a routine procedure, with a low incidence of complications. The procedure involves formation of three small sclerotomies, removal of the vitreous gel, and then immediate implantation of the OpRegen® into the subretinal space via a very small caliber cannula.

The subretinal implantation as described following vitrectomy is schematically depicted in [Figure 3](#)²³ below.

[figure not shown]

Figure 3: Subretinal Implantation After Vitrectomy

A surgical procedure manual describes the details of the procedures for vitrectomy and OpRegen® subretinal implantation.

[figure not shown]
²³ From ([Stout JT 2011](#)). (Note that in this schematic drawing, placement of the surgical ports is not anatomically accurate).

Detailed surgical procedure manuals provided to the sites describe the specifics of the individual procedures. All surgical implantation procedures will be video-recorded for subsequent analyses.

11.3.2.5 Post-Implantation Activities and Follow-Up

The surgery report and required procedure documentation will be completed, and the clinical trial records will be updated to accurately reflect the outcome of the transplantation.

Following OpRegen® implantation, subjects will remain in the recovery room or return to the ophthalmology department for close monitoring for safety until the subject is stable and meets all criteria for discharge.

The flowchart below (Figure 5) schematically shows the activities for OpRegen® implantation following vitrectomy as described above.

[figure not shown]
[figure not shown]

Figure 5: [Redacted] activities flowchart

Following OpRegen® implantation, using either surgical procedure, the subject may be hospitalized (if country specific requirement) for up to three days, per investigator discretion. After the surgery, the subject will be followed up for general health/ophthalmological complaints and safety. Any changes in overall health will be assessed and treated, as needed.

Post-surgery discharge will be performed at the discretion of the investigator according to the subject's general and ophthalmological condition. During the post procedure period and until end of study, a total of 14 visits will be performed. A total of 12 visits will be performed at site and two visits will be telephone visits ([REDACTED] and [REDACTED]).

[REDACTED]

[REDACTED]

[REDACTED], the following assessments will be performed at [REDACTED]:

- General safety assessments (AEs and concomitant) medications

- █ █
- General safety assessments (AEs and concomitant medications)
 - Vital signs
 - Physical examination
 - Dilated Fundus Examination
 - IOP
 - Slit Lamp Exam
 - Immunosuppression assessment
 - █ █
 - BCVA
 - Low Luminance BCVA (optional for cohort 4 subjects with low vision who are not able to perform this test and is not applicable for cohorts 1-3)
 - SD-OCT (central reading)
 - FAF (central reading)
 - CFP (central reading)
 - Microperimetry (central reading) cohort 3 [optional], but is required for all █ subjects and all cohort 4 US-treated subjects

- █ █
- General safety assessments (AEs and concomitant medications)
 - Vital signs
 - Physical examination
 - Dilated Fundus Examination
 - IOP
 - Slit Lamp Exam
 - Subject will be instructed to take “per protocol medications” and to contact the site in case of any general or ophthalmological conditions.
 - BCVA
 - Low Luminance BCVA (optional for cohort 4 subjects with low vision who are not able to perform this test and is not applicable for cohorts 1-3)
 - SD-OCT (central reading)
 - FAF (central reading)
 - CFP (central reading) – optional, as per investigator discretion.
 - CBC (including differential)
 - Chemistry (including Serum Electrolytes)
 - Coagulation
 - Urinalysis
 - Rheumatology (including ESR and CRP)
 - HLA typing if not done previously

- [REDACTED]
- General safety assessments (AEs and concomitant medications)
 - Vital signs
 - Dilated Fundus Examination
 - IOP
 - Slit Lamp Exam
 - Immunosuppression assessment
- [REDACTED]
- BCVA
 - Low Luminance BCVA (optional for cohort 4 subjects with low vision who are not able to perform this test and is not applicable for cohorts 1-3)
 - SD-OCT (central reading)
 - FAF (central reading)
 - CFP (central reading)
 - Microperimetry (central reading) cohort 3 [optional], but is required for all [REDACTED] subjects and all cohort 4 US-treated subjects
 - CBC (including differential)
 - Chemistry (including Serum Electrolytes)
 - Coagulation
 - Urinalysis
 - Rheumatology (including ESR and CRP)
 - HLA typing if not done previously

- [REDACTED]
- [REDACTED]
- [REDACTED]
- General safety assessments (AEs and concomitant medications)
 - Vital signs
 - Dilated Fundus Examination
 - IOP
 - Slit Lamp Exam
 - Immunosuppression assessment
 - BCVA
 - Low Luminance BCVA (optional for cohort 4 subjects with low vision who are not able to perform this test and is not applicable for cohorts 1-3)
 - SD-OCT (central reading)
 - FAF (central reading)
 - CFP (central reading) – optional, as per investigator discretion

- [REDACTED]
- General safety assessments (AEs and concomitant medications)
 - Vital signs
 - Physical examination
 - Dilated Fundus Examination
 - IOP
 - Slit Lamp Exam
 - Immunosuppression assessment
 - BCVA
 - Low Luminance BCVA (optional for cohort 4 subjects with low vision who are not able to perform this test and is not applicable for cohorts 1-3)
 - Microperimetry (central reading) cohort 3 [optional], but is required for all [REDACTED] subjects and all cohort 4 US-treated subjects
 - SD-OCT (central reading)
 - FAF (central reading)
 - CFP (central reading)
 - [REDACTED]
 - CBC (including differential)
 - Chemistry (including Serum Electrolytes)
 - Coagulation
 - Urinalysis
 - Rheumatology (including ESR and CRP)
 - Malignant hematological transformation
 - HLA typing if not done previously
- [REDACTED]
- [REDACTED]
- [REDACTED]

- [REDACTED]
- General safety assessments (AEs and concomitant medications)
 - Vital signs
 - Physical examination
 - Dilated Fundus Examination
 - IOP
 - Slit Lamp Exam
 - Immunosuppression assessment
 - BCVA

- Immunosuppression assessment (optional, only if subject is still prescribed mycophenolate mofetil, per investigator discretion)
- BCVA
- Low Luminance BCVA (optional for cohort 4 subjects with low vision who are not able to perform this test and is not applicable for cohorts 1-3)
- SD-OCT (central reading)
- FAF (central reading)
- CFP (central reading)
- CBC (including differential)
- Chemistry (including Serum Electrolytes)
- Coagulation
- Urinalysis
- Rheumatology (including ESR and CRP)
- HLA typing if not done previously

[REDACTED]

[REDACTED]

[REDACTED]

This visit will be a telephone visit during which the subject will be asked general questions regarding his/her health and visual condition. Following phone safety assessment, the subject may be invited to perform further systemic and/or ocular testing, as required. These visits will be defined as unscheduled visits.

[REDACTED] **END OF STUDY/ EARLY DISCONTINUATION**

This visit is for subjects who completed the whole study duration of [REDACTED] post-implantation of OpRegen®, or for subjects who prematurely discontinued planned [REDACTED] study (early termination criteria, see [Section 12](#)).

- General safety assessments (AEs and concomitant medications)
- Vital signs
- Physical Examination
- Dilated Fundus Examination
- IOP
- Slit Lamp Exam
- Immunosuppression assessment [REDACTED]
- BCVA
- Low Luminance BCVA (optional for cohort 4 subjects with low vision who are not able to perform this test and is not applicable for cohorts 1-3)

- SD-OCT (central reading)
- FAF (central reading)
- CFP (central reading)
- Microperimetry for cohort 3 [optional], but is required for all [REDACTED] subjects and all cohort 4 US-treated subjects
- NEI-VFQ25 (interviewer version)
- Functional Reading Independence (FRI) index
- Reading speed test
- Fluorescein Angiography (central reading)
- CBC (including differential)
- Chemistry (including Serum Electrolytes)
- Coagulation
- Urinalysis
- Rheumatology (including ESR and CRP)
- Malignant hematological transformation
- HLA typing, if not done previously
- ECG

12. CRITERIA FOR EARLY TERMINATION/ DISCONTINUATION

Subjects who discontinue early or are prematurely discontinued from the study should be followed and treated by the study Investigator in a customary manner. All of the Early Discontinuation assessments (Section 11.7) should be performed before discontinuation of the subject, if possible.

All subjects have the right to withdraw consent and discontinue participation without prejudice at any time during the study. The Investigator, in conjunction with the Sponsor, may also discontinue the subject from participation in the study at any time if both consider discontinuation to be in the subject's best interest.

Reasons for withdrawal of the subject prior to [REDACTED] must be stated in the CRF and in the source documentation for all study subjects who were enrolled in the study.

A subject may withdraw or be withdrawn from the study for the following reasons:

1. Subject withdrawal of consent
2. Sponsor requests subject to be withdrawn
3. Request of primary care physician or investigator
4. Non-compliance

5. Protocol Violation of inclusion or exclusion criteria, if, in the opinion of the Investigator and the Sponsor, the violation would significantly compromise data interpretation
6. Loss to follow-up/failure to return
7. AE/Experience
8. Subject requires additional therapy which is prohibited according to the protocol
9. Disease progression
10. Death
12. Termination of the study by the Sponsor
11. Other

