4.3 TREATMENT APPROACHES

There is currently no effective or approved treatment for dry-AMD. Prophylactic measures include vitamin/mineral supplements. These reduce the risk of developing wet AMD but do not affect the development or progression of GA.

There are currently no FDA approved treatments for GA secondary to AMD. GA is a chronic, progressive condition that leads to central blind spots and often, permanent loss of vision.

The development of several investigational agents has been halted because of disappointing results, however intensive AMD research continues, raising hopes for improved treatments. Though multifactorial, the underlying mechanism of non-neovascular AMD (dry-AMD) is the death of RPE cells. The RPE comprise a single layer of cells, which perform many functions necessary for healthy photo transduction (Strauss O 2005) and any dysfunction in these activities may lead to vision loss. Cell transplantation of healthy RPE to replace dystrophic or lost RPE has been considered a potential therapy to preserve or even restore vision loss.

The Sponsor uses a GMP-compliant hESC line, ethically approved for inclusion in the NIH Human Embryonic Stem Cell Registry, for derivation of the RPE cells, using the directed differentiation approach, described in the subsequent section.

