9.2 DISALLOWED CONCOMITANT MEDICATIONS

The subjects should be instructed to discontinue medications that may alter coagulation, including aspirin and aspirin-containing medications, 7 days prior to the implantation of OpRegen. They should be guided to discuss the risks associated with this discontinuation with their primary physician. Decisions regarding the timing of restarting these medications will be at the discretion of the Principal Investigator.

Anti VEGF intraocular injections are contraindicated when given as a treatment for Wet AMD. However, if subject was treated with Anti VEGF intraocular injections as a short-term therapy for an indication other than Wet AMD (or disease which is defined as exclusion criteria) more than

⁶ In the case of any suspected malignancies at screening, patient should be referred to appropriate medical specialist.

12 months prior to study baseline, patient may be eligible after being discussed with Study Medical Monitor.

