14.2 ASSESSMENT OF POTENTIAL OPHTHALMOLOGICAL CLINICAL EFFECT

Visual assessments will be performed prior to and after OpRegen® implantation in order to determine whether OpRegen® implantation has an effect on visual parameters.

Potential efficacy will be evaluated, but not limited by determining the rate of the GA progression, retinal sensitivity to light in the engrafted regions and changes in visual acuity.

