## 6.3 Procedures for Handling Missing Data and Outliers

Missing or incomplete dates will be imputed per [Section 4.1.1](#) for the purposes of determining treatment emergence. All other missing data will not be imputed, unless otherwise noted.

All unscheduled visit data will be included in data listings. In the data summary tables, the presence of missing data will be indicated by the inclusion of a 'missing' category with categorical data, and a count and percentage of missing observations for continuous numeric data, where applicable.

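### Protocol Section 12 allows withdrawal from the study for undefined disease progression, which is itself an efficacy outcome, so dropout can depend on the outcome

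*Protocol*

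**What the plan says.** Protocol Section 12 opens its list with "A subject may withdraw or be withdrawn from the study for the following reasons". Two entries matter here: "8. Subject requires additional therapy which is prohibited according to the protocol" and "9. Disease progression". Progression is not defined, no threshold is set, and neither eye is named. Subjects who leave are then followed in the customary way. An early-discontinuation visit is requested if possible, and the protocol's list for that visit includes BCVA, SD-OCT, FAF, CFP and FA.

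Protocol 4.3 states that "GA is a chronic, progressive condition that leads to central blind spots and often, permanent loss of vision". Protocol 14.2 states that "Potential efficacy will be evaluated, but not limited by determining the rate of the GA progression", and 7.3.4 lists change in GA area of the study eye and change in BCVA as efficacy endpoints. Each subject receives one implantation (Protocol 10).

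On therapies, Protocol 9.2 says "Anti VEGF intraocular injections are contraindicated when given as a treatment for Wet AMD". It then turns to injections given before baseline and whether such a patient may still be eligible.

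On missing data, SAP 6.3 says "All other missing data will not be imputed, unless otherwise noted" (imputation of dates is dealt with separately). Protocol 22.6 instead names the last observed value, where appropriate. SAP 9.0 bases the short-term and Year 5 analyses on subjects who have the assessment at that time. SAP 7.1.1 tabulates reasons for termination only before the 1 Year Visit.

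**The concern.** GA is expected to progress, and its progression is what the efficacy analysis measures. A rule that lets a subject leave because of progression lets retention depend on the endpoint. In a repeat-dose trial, such a rule may at least serve to stop a failing treatment. Here the implant cannot be stopped, so exit chiefly ends protocol imaging and visits.

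The SAP has no step that would offset this. Later visit means and the Year 5 analysis would describe only the eyes that stayed, and no sensitivity analysis for progression-related exits is planned. Protocol 6.2 says efficacy will be explored in about 12 Cohort 4 eyes and may be used in designing later studies, so one or two such exits could matter. Safety follow-up, the primary objective, would also become thinner in the subjects who left.

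**Working it through.** **Inputs from the documents**
- Cohort sizes 3, 3, up to 6 and about 12 (Protocol 8.1.1). The sum is 3 + 3 + 6 + 12 = 24, which reproduces the stated total. It is a plain sum, not a powered figure.
- No SD, growth rate, inter-eye correlation or withdrawal rate is given. The size of any bias therefore cannot be derived from the documents, and what follows is an illustration under stated assumptions.

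**Step 1. What is kept and what is lost when a subject exits for progression**
- Kept: all data captured before exit (Protocol 22.2.1; SAP 6.1) and, if it takes place, one exit visit with imaging.
- Lost: later scheduled imaging of both eyes, and the subject's place in the Year 5 analysis (SAP 9.0).
- Undetermined: the GA annual rate. SAP 11.0 plans a figure and a listing for it, but no rule says how the rate is derived or whether exit values enter.

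**Step 2. Shift in the completer mean (worst case)**

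Assume normally distributed growth across n eyes, and that the k fastest study eyes leave and contribute nothing afterwards. In SD units,

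shift = -(sum of the k largest expected order statistics) / (n - k).

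From 200,000 simulated samples:

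| k lost | n = 12 | n = 24 |
|---|---|---|
| 1 | -0.147 | -0.084 |
| 2 | -0.273 | -0.156 |
| 3 | -0.392 | -0.223 |

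**Step 3. As a percentage of mean growth, n = 12**

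Assume a between-eye coefficient of variation of 30% to 70%, with negative growth set to zero. The last column freezes each leaver at the value reached after 25% or 50% of follow-up, as a last-observed-value rule would.

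| k lost | Understatement, no imputation | Understatement, last observed value |
|---|---|---|
| 1 | 4% to 10% | 6% to 13% |
| 2 | 8% to 18% | 12% to 24% |
| 3 | 12% to 26% | 17% to 33% |

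The protocol's last-observed-value rule therefore does not remove the problem.

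**Step 4. Treated-minus-fellow contrast**

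Assume equal SDs in the two eyes and inter-eye correlation rho. Let d be the fall from Step 2.
- If the study eye triggers exit, the treated mean falls by d and the fellow mean by rho × d, so the contrast shifts by -d(1 - rho). For k = 3 this is -0.392 × 0.5 = -0.20 SD at rho = 0.5, and -0.392 × 0.3 = -0.12 SD at rho = 0.7. For k = 2 it is -0.273 × 0.5 = -0.14 SD at rho = 0.5, and -0.273 × 0.1 = -0.03 SD at rho = 0.9.
- If the fellow eye triggers exit, the roles swap and the contrast shifts by +d(1 - rho), against the treatment.

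**Step 5. Comparison with sampling error**

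With 12 eyes the standard error of the mean is 1/√12 = 0.29 SD, and the 95% half-width is about 0.64 SD. Even the k = 3 shift lies inside that interval.

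**The case against.** The strongest reply is that Section 12 is permissive and reads in part as a list of reason codes. Death, loss to follow-up and a catch-all entry sit beside the two at issue, and reasons must be recorded in the CRF. No progression-based exit is documented. All efficacy data are to be listed for every subject (SAP 7.1.10), and an Early Discontinuations table and listing are planned (SAP 11.0). With 24 subjects, such an exit would be noticed. Efficacy is descriptive, and the illustration assumes perfect selection of the fastest eyes. All of this stands, and it limits the point to a risk.

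Three stronger readings are tempting, and the documents do not support them.
- *A reader might infer that the plan biases the result toward benefit.* No eye is named, and the treated-versus-fellow contrast reverses if the fellow eye prompts the exit.
- *A reader might infer that subjects who convert to wet AMD must leave through reason 8.* Section 9.2 reads partly as an eligibility rule, no section says a converted subject exits, and FA is foreseen during follow-up for suspected conversion. Nor does anything tie conversion to the fastest GA growth.
- *A reader might infer that late safety data are lost.* Events that are serious or caused discontinuation are followed to resolution or stability (Protocol 14.1). After early termination, SAEs are collected for at least 12 weeks after the last per-protocol drug, then only if judged related (Protocol 21.1.2). New unrelated events and scheduled imaging drop away, so the data are thinner, not absent.

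It is also true that exit in the early months could bear on per-protocol immunosuppression. The synopsis, however, already allows that treatment to be modified without the subject leaving the study.

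**Conclusion.** The point holds as a risk of outcome-dependent dropout, not as a demonstrated bias. The protocol permits study exit on an undefined criterion that overlaps an efficacy outcome, and the planned analyses do not protect against it. If the study eye triggers exit, GA growth in treated eyes looks slower: by 0.15, 0.27 or 0.39 SD when the fastest 1, 2 or 3 of 12 eyes are lost, and by that times (1 - rho) for the contrast with the fellow eye.

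These are worst-case figures. They rest on assumed normal growth, perfect selection and no later contribution from leavers. The percentages also rest on an assumed coefficient of variation, and the contrast figures on an assumed correlation and equal SDs. Whether reason 8 acts in the same way cannot be settled until Section 9.2 is clarified. The change is worth making because it is cheap and specific.

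**What to change.** **Protocol**
- In Section 12, remove disease progression as a reason to leave the study. State that progression, or starting another therapy, does not by itself end scheduled study assessments. Leave the consent, best-interest, adverse-event, non-compliance and other exits as they are.
- Reconcile Section 9.2 with Section 12 on the study status of a subject who converts after implantation. No view is taken here on any therapy.
- Record conversion to wet AMD and any later ocular therapy, with dates.

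**SAP**
- Use all available GA and BCVA data, including exit-visit values, and state how the GA annual rate is derived.
- Show results as observed and, separately, excluding visits after such therapy.
- Reconcile Protocol 22.6 (last observed value) with SAP 6.3 (no imputation).
- Tabulate exit reasons through Year 5, not only before the 1 Year Visit.

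**Cost.** One short amendment, a few SAP paragraphs and one extra display; no new visits. The SAP dated 12 October 2022 describes all 24 subjects as treated, so an amendment would reach only the follow-up that remains. SAP changes are open until database lock (SAP 2.0). The downside is that some retained visits come from eyes given another therapy, which the second display handles.
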